Safety outcomes. We will collect the following before the iTBS sessions: hours of sleep, UDS/TLFB, breathalyzer, the AE/SAE form, pain, and the Cocaine Selective Severity Assessment (CSSA – a measure of withdrawal). The AE/SAE form and pain will also be completed after the iTBS session. See Table 2 for the Study Visit Timeline.

[figure not shown]

Table 2. Study Visit Timeline – Pilot Study

[figure not shown]
Assessment	Length of Time	Details
Assess safety:	5-10 min	UDS, TLFB, pregnancy, sleep, CSSA, C-SSRS, AE/SAE form
Cognitive Assessment	10 min	MoCA
Fit EEG cap:	30 min	Measure & place cap on head, gel electrodes
Complete EEG Session 1:	35 min	Resting EEG, Doors Task, Picture Viewing Task
Assess rMT:	10 min	Collect resting motor threshold
iTBS Session 1:	3 min	iTBS to dmPFC or sham iTBS
Rest:	15-20 min	Sit quietly
iTBS Session 2	3 min	iTBS to dmPFC or sham iTBS
Assess safety:	5-10 min	AE/SAE form
Cognitive Assessment	10 min	MoCA
Complete EEG Session 2:	35 min	Resting EEG, Doors Task, Picture Viewing Task

Main Trial

Design. The proposed study will use a within-subjects cross over design as shown in *Fig 2*. Non-treatment-seeking adults with a primary CUD diagnosis (N = 75) will complete screening and baseline assessments prior to completing three separate iTBS days (sham, dlPFC iTBS, or dmPFC iTBS), order counterbalanced across participants. On each day, EEG will be collected before and after 3 iTBS successive sessions (15-minutes between sessions). Days will be spaced at least 24-hours apart and will be completed within 2 weeks. We will aim to consent 115 participants to achieve 75 completed.

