[name] (*Biosketch*), will perform the TMS at the Treatment-Resistant Mood Disorders Program at UTHealth, adjacent to the CNRA. TMS will be delivered with a MagVenture Mag Pro R30 with the Cool-B70 A/P coil with active liquid cooling and active/sham sides (Farum, Denmark). A member of the CNRA not involved in the study will be the only person aware of the counterbalanced order and will program the system to ensure double blinding. For dlPFC, we will measure position F3, using probabilistic EEG placement. For dmPFC, we will measure approximately 25% of the nasion-inion distance, or Talairah coordinates X 0 Y+60 Z+60^{32,98}. The first session will begin with the acquisition of the resting motor threshold (rMT; lowest stimulus intensity that elicits a visible twitch on 50% of the trials) on the contralateral hand. iTBS (triplet 50 Hz bursts, repeated at 5 Hz, 2 sec on and 8 sec off; 600 pulses per session) will be delivered at 110% of the rMT and will last ~3 minutes. The amplitude of the TMS can be lowered if the participant cannot tolerate the stimulation. The stimulation will start at a lower percentage and ramp up over time to acclimate participant to the feeling of stimulation. Each participant will receive 3 sessions per visit with a 15-20 minute interval between sessions to increase the likelihood of detecting acute effects¹⁰⁰. Participants will complete the EEG protocol before the first iTBS session (baseline) and immediately following stimulation sessions (*Table 1*).

Measures.

Baseline Measures. Urine samples will be collected at each study visit and tested for the cocaine metabolite, benzoylecgonine (BE) and other drugs of abuse. Samples containing ≥ 300 ng/ml of BE will be considered positive. Additionally, self-reported substance use will be assessed using the Timeline Follow Back¹⁰² to assess cocaine use severity (number of days used in the past 30 days). Impulsivity will be measured with the Barratt Impulsiveness Scale (BIS-11)¹⁰⁶. Cocaine craving (below) will also be measured at baseline.

Table 3. Schedule of Activities by Visit (Order of Study Visit Number counterbalanced and randomized across participants) Main Trial

		Sham	dmPFC ¹	dlPFC ²
Study Visit	Intake/Baseline	1	2	3
Screening Measures				
Informed Consent	X			
SCID DSM-5	X			
Addiction Severity Index	X			
Drug History KMSK	X			
TMS Safety Screen	X			
Safety Measures				
Urine Pregnancy Test (UPT)	X	X	X	X
Urine Drug Screen (UDS)	X	X	X	X
Breathalyzer	X	X	X	X
Vitals	X	X	X	X

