Statistical Modeling. Analyses will rely on **generalized linear modeling (GLM)** with **multilevel (GLMM)** components where necessary to evaluate predictor-outcome relationships. These models may fit normally or non-normally distributed outcomes as needed (e.g., Binomial with logit link for dichotomous outcomes). GLMM may also account for correlated observations via inclusion of random effects (e.g., a level 2 intercept). **Preliminary analyses** will use GLM to evaluate relationships between baseline sample characteristics, predictors, and outcomes prior to formal hypothesis testing. **Confounders** are defined as any sample characteristics that demonstrate relationships with both the predictor and outcome in a given model^{120,121}. Subsequent models will be tested with and without adjustment for each potential confounder; if resulting inferences are different, we will report both models; otherwise, we retain the simpler model. **Moderation analyses** will evaluate the potential influence of essential covariates and other baseline sample characteristics (including sex) by examining their higher-order interactions with model predictors. Analyses will be performed in R¹²² via packages lme4¹²³, rstan¹²⁴, and brms¹²⁵.

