Modeling Assumptions. Evaluation of assumptions for frequentist models will use graphical evidence (e.g., residual plots) and formal statistical tests. Bayesian convergence and modeling assumptions will be evaluated by effective sample size, scale reduction factors ("rhat"), and posterior predictive checking. Violated assumptions will be addressed via model re-specification, variable transformation, robust estimation, stratification, and/or coefficient scaling where appropriate. **Intention-to-treat (ITT)** primary analyses will include all randomized participants; follow-up analyses may evaluate modified ITT samples should specific participants merit exclusion (e.g., randomized but never initiated the trial). A per protocol analysis will complement the primary ITT analysis as due diligence. **Missing data** patterns will be evaluated using Little's Test of Missing Completely at Random (MCAR)¹³⁶ for continuous outcomes and the Park and Lee approach¹³⁷ for discrete outcomes. Models will handle missingness via maximum likelihood, explicit modeling of missingness¹³⁸, and/or imputation with sensitivity analyses to evaluate the robustness of findings. Each approach is

robust to ignorable missingness (i.e., missing completely at random and missing at random). Pattern-mixture modeling will be used to address identified non-ignorable missing data patterns¹³⁹.

Specific Analyses

All statistical models (described below) will account for correlated observations via the best-fitting structure of random effects (i.e., lowest information criteria) found when fitting level-2 intercepts and/or slopes) for repeated measures (where necessary) and statistically control for potential confounders as defined above. Outcome variables will be modeled as difference scores to account for the pre/post design (i.e., post-iTBS minus pre-iTBS).

Hypothesis 1a (Primary): Active iTBS relative to sham will increase the amplitude of the RewP/delta power to rewards compared to non-rewards. GLMM will model the change in amplitude of the RewP/delta power to rewards as a function of iTBS condition, with random effects to account for repeated measures.

Hypothesis 1b (Exploratory): iTBS to dmPFC will result in a greater increase in the RewP/delta power compared to dPFC. Follow-up testing of the model described above for Hypothesis 1a will evaluate pairwise comparisons between iTBS conditions.

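### Test-day order is counterbalanced, but no main-trial model includes visit; prespecifying it as a fixed factor costs almost nothing and gains precision and some protection against uneven dropout

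*Combined protocol and SAP*

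**What the plan says.** **Design.** Under Main Trial, Design, each participant has three stimulation days (sham, dlPFC, dmPFC), with "order counterbalanced across participants". The heading of Table 3 adds "Order of Study Visit Number counterbalanced and randomized across participants". The number of orders is not stated.

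**Models.** Under Analysis Plan, Main Trial, Specific Analyses, each outcome is the change from before to after stimulation on that day. For Hypothesis 1a, "GLMM will model the change in amplitude of the RewP/delta power to rewards as a function of iTBS condition", with random effects for repeated measures. Hypothesis 2a has the same form for LPP bias. Hypotheses 1b and 2b are pairwise follow-ups of those two models, and 3a adds interactions with baseline predictors. No model has a visit, period or sequence term.

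**General rules.**
- Statistical Modeling defines confounders as "any sample characteristics that demonstrate relationships with both the predictor and outcome in a given model".
- Specific Analyses says the models will "account for correlated observations via the best-fitting structure of random effects", chosen by information criteria.
- Modeling Assumptions allows re-specification if assumptions fail, but names no term.

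**Analysis set and losses.** Intention-to-treat "primary analyses will include all randomized participants". Under Design: "We will aim to consent 115 participants to achieve 75 completed".

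**Pilot.** Two test days in counterbalanced order, five participants. The models use time, location and, for the LPP, image type. Time there means before versus after stimulation, not visit.

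**The concern.** A crossover that balances order normally carries the period into the analysis. Here none of the general rules supplies it. Visit is not a sample characteristic and, when orders are balanced, it is unrelated to condition, so the confounder rule passes it by. The information-criterion rule selects random effects only. The re-specification clause is reactive.

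Change scores deal with part of the problem: a visit shift common to the pre and post recordings cancels. A visit effect on the change itself, for instance from growing familiarity with the same tasks, does not cancel.

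Two things are at stake. With balanced orders that variation goes into the residual and costs precision. If participants leave after randomisation at rates that depend on their order, condition and visit become correlated, and counterbalancing no longer fully protects the active-versus-sham contrast. Adding visit only after seeing the data would be an open analyst choice on the primary hypotheses.

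**Working it through.** **Inputs from Sample Size and Power Analysis and Design:** N = 75, three conditions, Cohen's f = 0.149, r = 0.50, two-tailed alpha 0.05, stated power 80%; 115 consented for 75 completed.

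**Assumed:** a linear visit effect on the change, d = difference between visit 1 and visit 3 in SD of the change score. The documents give no value, so a range is shown.

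**1. The plan's own figure.** For a within-factor repeated-measures F test, lambda = f² × N × m / (1 − r) = 0.149² × 75 × 3 / 0.5 = 9.99. On F(2, 148) power is 0.8067. The stated 80% reproduces.

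**2. Price of adding visit when visit does not matter.** Error df fall from 148 to 146. Power is 0.8065.

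**3. Gain with balanced orders.** Visit means of −d/2, 0 and d/2 have a sum of squares of d²/2 per participant. Left unmodelled, they add 75 × (d²/2) / 148 to the within-participant residual variance of 1 − r = 0.5. At d = 0.3 this is 75 × 0.045 / 148 = 0.0228.

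Reading A, r = 0.50 is net of visit: omitting visit divides lambda by 1 + added variance / 0.5 (1.046 at d = 0.3). Reading B, r = 0.50 already contains visit: fitting visit multiplies lambda by 0.5 / (0.5 − added variance).

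| d (SD) | A: power without visit | B: power with visit |
|---|---|---|
| 0.10 | 0.805 | 0.809 |
| 0.20 | 0.798 | 0.815 |
| 0.30 | 0.788 | 0.826 |
| 0.50 | 0.755 | 0.859 |

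Under A, power with visit stays at 0.8065. Under B, power without visit stays at 0.807. The A column scales lambda, which is an approximation. The doubly noncentral F gives 0.800, 0.791 and 0.761 at 0.2, 0.3 and 0.5 SD, and simulation of a balanced Latin square gives 0.790 at 0.3 SD. Under A, power drops below 0.80 from about d = 0.18 (approximation) or 0.2 (doubly noncentral F). Without visit the one-df active-versus-sham test is conservative: type I error 0.045 at 0.3 SD and 0.038 at 0.5 SD.

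**4. Bias when orders are uneven.** Shares are the part of d that enters active versus sham. Six orders are assumed. For dropout: 115 starters spread evenly, compound symmetry with r = 0.50, generalised least squares on all available visits.

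| Case | Share without visit | Share with visit |
|---|---|---|
| Balanced orders | 0 | 0 |
| 75 completers split 13/12 over six orders | at most 0.02 | 0 |
| 35% leave, equal in all orders | 0 | 0 |
| 10% of sham-first, 20% of active-first leave after visit 1 / visit 2 | 0.021 / 0.012 | 0 |
| 20% of sham-first, 42% of active-first leave after visit 1 / visit 2 | 0.059 / 0.031 | 0 |

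The last row corresponds to about 40 of 115 leaving: (0.20 + 2 × 0.42) / 3 × 115 = 39.9. It is an upper bound, because the 40 losses include screen failures. At d = 0.3 the largest bias is 0.059 × 0.3 = 0.018 SD, about 6% of the d = 0.30 the trial seeks. In that case fitting visit raises the standard error of active versus sham from 0.0967 to 0.0970, or 0.3%.

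**5. Pilot.** The best split of five participants over two orders is 3:2, so (3 − 2) / 5 = 0.20 of any visit effect on the change enters the dmPFC-versus-sham contrast. If one participant in the smaller order does not finish, the share is (3 − 1) / 4 = 0.50.

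**The case against.** The strongest reply is that nothing in the documents shows this matters. No visit effect on the change is given or suggested, and post-minus-pre scoring already removes a shift common to both recordings. With balanced orders there is no bias, the test errs on the conservative side, and at 0.2 SD or less the power loss under Reading A is below one point. Under Reading B the stated 80% is untouched, and the text does not say which reading applies. All of this stands, and it is why the point is an improvement and not an error in the power statement.

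The bias argument needs a further assumption, that dropout differs by order. The 115-to-75 allowance counts from consent, which comes before the eligibility intake. Missed day-of requirements lead to rescheduling, and payments rise across visits to hold participants. Six orders are also an assumption: with three Latin-square orders, 75 divides evenly. These facts limit the likely size. They do not supply the missing term.

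One technical limit also stands. A visit factor removes only an additive visit effect. It does not deal with carryover between days, a visit-by-condition interaction, or dropout that depends on the outcome.

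Finally, the main trial is registered as a separate record, and for the pilot the plan itself disclaims estimates that generalise. The main trial's analysis plan is nevertheless in this document, and that is where the point has weight.

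**Conclusion.** The concern holds as a nearly free improvement. The design balances visit, the analysis leaves it out, and no rule in the plan restores it. The gain is conditional on an unknown visit effect on the pre-to-post change: negligible up to about 0.1 SD, around 2 points of power at 0.3 SD, and around 5 points at 0.5 SD, under either reading of r = 0.50. The protection is also modest in the dropout cases examined, at most 0.018 SD at a 0.3 SD visit effect, and it applies to additive visit effects only. Against this, the cost if visit is irrelevant is about 0.0001 in power. The stated 80% is not shown to be wrong, and the pilot part is minor and descriptive.

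**What to change.** **Main trial.** In Specific Analyses, prespecify visit (1, 2, 3) as a fixed factor in the change-score models for Hypotheses 1a to 3a, in both the frequentist and the Bayesian fits. In Sample Size and Power Analysis, state whether r = 0.50 is net of visit.

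**Pilot.** Report the realised split of orders, and add one sensitivity model with visit and visit × time.

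**Cost.** SAP wording and one extra pilot model; no new data and no change to the sample size. The statistical price in the main trial is the two error degrees of freedom, plus the 0.3% increase in standard error in the most uneven dropout case above.

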
Note. ¹EEG tasks are collected before and after 2 sessions of iTBS – 3 minutes of resting EEG data, the Picture Viewing Task, the Doors Task. ²iTBS – two sessions of iTBS, separated by 15-20 minutes rest. Either sham iTBS or iTBS to dmPFC. ³Safety Measures – hours of sleep, Cocaine Selective Severity Assessment (CSSA; withdrawal), and AE/SAE form will be collected prior to iTBS. AE/SAE form will be completed both before and after iTBS sessions. ⁴MoCA performed prior to 1st iTBS session and after 2nd iTBS session.
		

Payment and Compensation. Participants will be paid \$35 for the screening/intake visits, plus compensation for parking/bus passes. Participants will receive \$150 for each EEG/TMS evaluation days.

Baseline Screening. Participants will receive a psychiatric evaluation during the first week including a complete psychiatric diagnosis using the Structured Clinical Interview for DSM-5 (SCID-5) administered by trained licensed professional counselors under the supervision of a licensed clinical psychologist. Screening will include urine sample for urinalysis testing for drugs of abuse and pregnancy. In addition to the general evaluation, participants will complete the TMS Adult Safety Screen per Keel et al⁹⁷. Upon completion of this intake evaluation, eligible participants will be invited to participate in the study.

TMS Session. The PI or a trained research assistant/nurse under the supervision of [name] [name], will perform the TMS at the Treatment-Resistant Mood Disorders Program at UTHealth, adjacent to the CNRA. TMS will be

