delivered with a MagVenture Mag Pro R30 with the Cool-B70 A/P coil with active liquid cooling and active/sham sides (Farum, Denmark). A member of the CNRA not involved in the study will be the only person aware of the randomization results and will program the system to ensure double blinding.). For dmPFC, we will measure approximately 25% of the nasion-inion distance, or Talairah coordinates X 0 Y+60 Z+60^{32,98}. The first session will begin with the acquisition of the resting motor threshold (rMT; lowest stimulus intensity that elicits a visible twitch on 50% of the trials) on the contralateral hand. iTBS (triplet 50 Hz bursts, repeated at 5 Hz, 2 sec on and 8 sec off; 600 pulses per session) will be delivered at 80% of the rMT and will last ~3 minutes, consistent with current EEG-iTBS single day protocols^{73,99}. The intensity can be lowered if the participant cannot tolerate the stimulation. Each participant will receive 2 sessions with a 15-20 minute interval between sessions¹⁰⁰. Participants will complete the EEG protocol before the first iTBS session (baseline) and immediately following the two stimulation sessions. This will conclude participation for the pilot participants.

EEG Protocol. During the tasks described below, EEG electrode cap, amplified with BrainAmp MR and digitized using Brain Vision Recorder (Brain Products, Munich). Before collection, impedances will be maintained below 50 k(OHM). The sampling rate will be 500 Hz and data will be filtered with .1 Hz high-pass and 100 Hz low-pass filters. Resting data will be collected for 3 minutes (90-seconds eyes open and 90-seconds eyes closed). After collection, data reduction will be performed with a combination of programs including Brain Vision Analyzer 2, MATLAB (EEGLab; PCA Toolkit) and BESA. Both traditional windowed ERP (mean amplitude) and TFA approaches will be used to analyze the RewP. The LPP will be defined as the mean amplitude between 400-800ms post stimulus.

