Cue Reactivity. The Picture Viewing Task will be used to elicit the LPP, reflecting the motivational salience of a stimulus. During this task, participants are asked to view a slideshow of images including pleasant, unpleasant, neutral, and cocaine-related images⁶¹.

Cocaine Craving. Cocaine craving will be measured using the Minnesota Cocaine Craving Scale (MCCS)¹⁰³. The MCCS is a widely used and reliable self-report measure of craving for cocaine. It will be assessed before and after each iTBS session.

Behavioral Reward Learning. Participants will complete a Pavlovian Go/No-Go task to assess Pavlovian influences on instrumental learning¹⁰⁷⁻¹¹⁰. In the first “learning” phase, participants learn whether to press a button or withhold a response to receive a monetary reward or avoid a loss. In the second “transfer” phase, participants perform a forced choice task, where each of the predictive cues in the learning phase are paired with each other. Participants must select the “most rewarding” cue.

Delay Discounting and Cocaine Demand. Both delay discounting and cocaine demand are measures that provide information about cost-benefit trade-offs and are often associated with substance use outcomes. Previous studies have shown that TMS might alter these principles¹¹¹. The delay task will specifically measure delay discounting and will consist of 5 questions about whether the participant would hypothetically like to receive less money now or more money later¹¹². The cocaine purchasing task will be used to assess how much cocaine the participant would be willing to use given incremental cost of cocaine^{113,114}.

Safety/Other outcomes. We will collect the following day-of measures before iTBS sessions: Profile of Mood States (POMS)¹¹⁵, hours of sleep, Patient-Reported Outcomes Measurement Information System (PROMIS) Sleep Disturbance (SD) and Sleep-Related Impairment (SRI) short forms^{116,117}, UDS/TLFB, breathalyzer, withdrawal (Cocaine Selective Severity Assessment; CSSA¹¹⁸), and the TMS AE/SAE form. The TMS AE/SAE form will also be completed after iTBS sessions. The Montreal Cognitive Assessment (MoCA)¹⁰⁴ will be used to assess for changes in cognition and will be administered before and after the 3 iTBS sessions.

Analysis Plan

Pilot Study

Data Analytic Strategy.

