exclusionary. Hearing impairment can occur without protection; however, the risk of this is extremely low in this study, as proper hearing protection will be used. There is also a risk for manic switch or psychotic episode, especially in patients with bi-polar disorder. Individuals with bipolar disorder or schizophrenia/psychotic symptoms will not be included in the study. There are also risks associated with magnetic field effects on functioning of other medical devices, but individuals with any medical implant will be excluded from the study. While the risks associated with TMS in substance using populations is still being evaluated, there are now several studies showing safety of TMS for these populations^{3,24,25,27,29,30,40,143}. There is also a risk that TMS can affect cognitive functioning, such as working memory and executive function. However, the current literature on iTBS specifically is suggestive of improvement of cognitive functioning with iTBS to the prefrontal cortex, rather than harm. A recent systematic review reported that 6/8 iTBS studies showed significant improvements in working memory and executive function¹⁴⁴. There is also one study showing that iTBS to the prefrontal cortex improved both working memory and executive function in stimulant users¹⁴⁵. Other more common but milder risks include discomfort at the stimulation site, headache and neck pain, tingling, spasms, or twitching of facial muscles, and lightheadedness during the actual administration of TMS. These side effects usually rapidly disappear after stimulation. Sometimes headaches can persist after the TMS session is over and can be treated with over-the-counter medications.

Diagnostic Procedures. Items on certain questionnaires and interviews might be perceived as psychologically discomforting to some participants. While participants may be uncomfortable reporting these issues, the risks of serious sequelae are extremely low. There are also risks concerning loss of confidentiality.

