EEG Session. Participants in the EEG session may experience skin irritation from the placement of the sensors, which is usually minor and goes away after a few hours. The presentation of emotional images and drug images in the Picture Viewing Task (e.g., mutilations or violence) may cause an affective response, which typically subsides rapidly after image presentation. Participants are shown example images beforehand and agree to watch the slideshow. They can also ask for the slideshow to be stopped at any time. Participants may also feel tired or bored while participating in the EEG session.

Adequacy of Protection against Risks

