All Adverse events (AE) will be collected and reported to the PI on a daily basis. AEs are collected before and after the iTBS sessions on the study visit day. As most side effects are minor and disappear rapidly after iTBS administration, participants will be told to contact the study coordinator if side effects persist after treatment at home with over-the-counter analgesics. The study physician will be informed of any relevant AEs following TMS and will determine course of treatment or discontinuation of the study, if necessary. AEs will be reported to the CPHS on an annual basis. Serious adverse events (SAE) will be reported immediately (verbally within 24 hours) to the CPHS, DSMB, and to NIDA (if funded). A written report will follow within three days and will include: date of the AE, description of the AE, severity rating (Grade 1 to 4), assessment of cause, whether the AE indicates an increased risk for current or future participants, and whether changes to the informed consent form are necessary.

REFERENCES

2. Volkow ND, Wang G-J, Fowler JS, Tomasi D, Telang F. Addiction: Beyond dopamine reward circuitry. *Proc Natl Acad Sci*. 2011;108(37):15037-15042. doi:10.1073/pnas.1010654108

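### No adverse-event enquiry is scheduled after the visit-day iTBS forms, so later events on a participant's last test day are recorded only if the participant calls

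*Combined protocol and SAP*

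**What the plan says.** The collection rule appears in four places, and they agree.

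- Data and Safety Monitoring Plan, Safety Monitoring: "AEs are collected before and after the iTBS sessions on the study visit day".
- Pilot Table 1, note on safety measures: "AE/SAE form will be completed both before and after iTBS sessions".
- Pilot, Safety outcomes: "The AE/SAE form and pain will also be completed after the iTBS session".
- Main Trial, Safety/Other outcomes: "The TMS AE/SAE form will also be completed after iTBS sessions". Main-trial Table 3 has an intake column and three stimulation visits, with no column after the third.

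Pilot Table 2 gives the order within a visit. The second safety slot (AE/SAE form, 5-10 min) follows iTBS Session 2. The MoCA (10 min) and EEG Session 2 (35 min) come after it, and no later form is listed. The pilot TMS Session paragraph closes with the post-stimulation EEG and adds: "This will conclude participation for the pilot participants".

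For events after the participant has left, Safety Monitoring tells participants to get in touch with the coordinator when side effects have not cleared with analgesics taken at home. Potential Risks, TMS, says that most side effects fade quickly, but also: "Sometimes headaches can persist after the TMS session is over".

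**The concern.** A participant's earlier test day has two scheduled chances to reveal a late or lingering event: the form directly after iTBS and the pre-iTBS form at the next visit. The last test day has only the first. After it, capture is passive, and the stated trigger for a call leaves out a headache that begins on the way home and clears with an analgesic. Following the rule exactly therefore misses a kind of event that the protocol itself expects.

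These records are used. The DSM Board is to review adverse experience data and the balance of risk and benefit. The pilot is meant to test assessment procedures and implementation before a main trial that schedules more iTBS sessions per visit (three against two). Reporting a serious event within 24 hours also presupposes that someone on the study hears of it.

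**Working it through.** The plan gives no figure on this point to reproduce. The check sets the scheduled enquiries against the design and counts the days without a later one.

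**1. Enquiries after stimulation, by position of the test day**

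| Test day | Form directly after iTBS | Next visit's pre-iTBS form | Scheduled contact after leaving |
|---|---|---|---|
| Any but the last | yes | yes | none stated |
| Last | yes | none | none stated |

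The look-back at the next visit is at least 24 hours in the main trial, where days are spaced at least that far apart. For the pilot no spacing between test days is given, so its look-back is undefined.

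**2. Time on site after the last listed form (pilot Table 2)**

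MoCA 10 min + EEG Session 2 35 min = 45 min. Only part of this carries a risk that the protocol names: the Picture Viewing Task is one of three components of the EEG session, beside resting EEG and the Doors Task.

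**3. Days with no later scheduled enquiry**

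- Pilot: 5 participants × 2 test days = 10 days. Each participant has one last day, so 5/10 = 50%.
- Main trial, if 75 complete: 75 × 3 = 225 days, and 75/225 = 33%.

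**4. Split by condition**

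- Pilot: five participants cannot be divided evenly over two orders; the closest split is 3 and 2. If active iTBS is last for three, a later scheduled enquiry covers (5 − 3)/5 = 40% of active days and (5 − 2)/5 = 60% of sham days. If active is last for two, the figures swap.
- Main trial: with three conditions counterbalanced, each is last for about 75/3 = 25 participants, so 25/75, one third, of the days of every condition lack a later enquiry.

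These are shares of days, not of events. The documents give no rate of delayed events and no rate of spontaneous reporting, so the number of events missed cannot be derived from them.

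**The case against.** **No planned test is affected.** A reader might infer that the comparison of active with sham is biased. The documents do not support that. The pilot analysis models RewP, LPP, craving, pain and MoCA; neither analysis plan contains an AE comparison between conditions. The pilot is for feasibility, and its estimates are not expected to generalise. The main trial's counterbalancing makes the loss about equal across conditions. This objection stands in full, and the point is confined to completeness of safety capture.

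**Several named risks have their own safeguards.** The protocol states: "There is also a risk for manic switch or psychotic episode, especially in patients with bi-polar disorder". The text that follows keeps people with bipolar disorder or psychotic symptoms out of the study, so this is a poor example of a missed event. For the emotional images, the risk section says they "may cause an affective response, which typically subsides rapidly after image presentation", and the protection section has participants report a bad reaction, stops the task and arranges a therapist meeting before they leave. Skin irritation is described as minor and clears within hours. It would be wrong to infer that such reactions pass unobserved, or that all 45 minutes consist of risky procedures. Persisting headache remains, and it is enough for the point.

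**Table 2 is not a full schedule.** It omits post-iTBS pain and the craving scale, which are stated elsewhere. An end-of-visit form could therefore exist in practice, but no section provides for one.

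**Other wording could be read more widely.** Safety Monitoring has AEs gathered and passed to the principal investigator daily, the protection section says milder side effects are monitored, and physicians can be reached by phone. None of these sets a contact with the participant after the visit.

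**Misattribution is not shown.** A reader might infer that late events will be filed under the wrong condition. The AE form is not in the documents and may record onset, an event on a pre-iTBS form plainly precedes that day's stimulation, and written SAE reports carry date and cause. What can be said is that no attribution rule is stated.

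**Conclusion.** The gap is real and modest. As written, AEs are actively asked about only before and directly after iTBS on the visit day. For 5 of 10 pilot days, and 75 of 225 main-trial days if 75 complete, anything later reaches the record only through a call from the participant, and that call is requested only for side effects that outlast home analgesics. Scheduled capture is therefore incomplete and depends on visit order.

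In the pilot, later scheduled coverage is 40% of days for one condition and 60% for the other under the closest possible counterbalance. In the main trial the loss is about one third of days in every condition, which means under-recording and not imbalance. The absence of a form after EEG Session 2 is established for the pilot's listed timeline only. The main-trial text does not place its post-iTBS form relative to the EEG. The counts assume that every participant completes all test days and that the next visit's pre-iTBS form picks up events since the previous visit.

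**What to change.** Three additions, none of which touches stimulation, endpoints or clinical management:

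1. Keep the AE/SAE form directly after iTBS and repeat it at the end of the visit, after EEG Session 2. Moving the form instead of repeating it would lose the immediate post-stimulation check.
2. Add one brief scheduled AE contact by existing staff after every test day, including the last, at the same interval after sham and active days. The investigators should set the interval.
3. Record onset time, and state that an event first reported on a later visit's pre-iTBS form is assigned to the preceding session if it began after that session.

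The cost is a few minutes per visit and one short call per test day: 5 × 2 = 10 calls in the pilot, and 75 × 3 = 225 in the main trial if 75 complete. Inclusion already requires details for two contact persons, which helps in reaching participants. A few more minor AEs will be recorded.
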